8.10.2 Procedures for discontinuation of a subject/patient from the study

A subject/patient who prematurely discontinues participation in the study will always be asked about the reason(s) for discontinuation and the presence of any AEs. If possible, they

will be seen by the Investigator and assessed according to the procedures scheduled for the follow-up visit/early termination. Any ongoing AEs will be followed as described in Section 10.5.8.

8.10.3 Subject replacement

Subjects who are prematurely withdrawn from the study may not be replaced during the course of the study.

8.11 Randomization

On study Day 1 (Visit 2), the subjects will be randomised to a treatment sequence. As this is an open study, the treatments to which each subject is allocated for the first dose administrations will be recorded in the eCRF. A computer-generated randomisation list will be created using SAS Proc Plan, SAS Version 9.4. The randomisation list will contain subject number, treatment sequence, period, and treatment.

The randomisation list will be generated by CTC or delegate and provided to the packing company. The original randomisation list will be kept by the randomiser. A copy of the randomisation list will be provided to the clinic. A coded copy of the randomisation list will be generated, i.e. a list where the treatment is blinded and this coded list will be provided to the bioanalytical laboratory and to the pharmacokineticist.

9 TREATMENTS

9.1 Identity of investigational products

The investigational products (IP), both test- and reference products are supplied by Swedish Match AB

9.1.1 *Test products*

- 1= ZYN® Smooth containing 6 mg nicotine per portion
- 2= ZYN® Smooth containing 8 mg nicotine per portion
- 3= ZYN® Wintergreen containing 6 mg nicotine per portion
- 4= ZYN® Smooth containing 6 mg nicotine per portion (lower lip)

9.1.2 Reference products

- 5= Swedish portion snus, General PSWL (8 mg nicotine/g) 2x1.0 g
- 6= American moist snuff, Longhorn Pouch Natural (12 mg nicotine/g) 1.5 g
- 7= American moist snuff, Longhorn Pouch Wintergreen (12 mg nicotine/g) 1.5 g

9.2 Packaging and labelling

The IP will be manufactured and packaged in compliance with the Swedish law on food production.

The IP will be transferred from the original container, weighed and individually packaged in identical sealed food approved test containers at the Swedish Match analytical lab. The containers will be labeled with unique identification numbers by Swedish Match in accordance with the randomisation list.

9.3 Conditions for storage

The IP will be stored in an access-controlled storage area at CTC, as per storage conditions specified by the Sponsor.

Temperature logs will be kept for the area where the IP is stored. The temperature should be noted on a daily basis (working days only unless automatic temperature readings are available).

9.4 Dispensing and accountability

The IP will be dispensed as per the randomization schedule by site personnel.

CTC AB and the Investigator will maintain a Drug Dispensing Log detailing the dates and quantities of IP received, dispensed to and used by each subject as well as IP returned or destroyed at the end of the study. Any discrepancies between dispensed and returned IP must be explained and documented. Products deliberately and/or accidentally destroyed by the Investigator or the subject/patient must be accounted for.

9.5 Treatment administration

A single dose will be given on the morning of each study day.

9.6 Continuation of treatment with Investigational Product

In this study the healthy volunteers who participate will have no medical benefit from the treatment and thus there will be no treatment with investigational or reference products after end of study participation.

9.7 Treatment compliance

All IP will be administered at the research clinic under medical supervision to ensure compliance.

9.8 Return and destruction of investigational products

Any unused IP will be destroyed at the study site. Empty containers will be destroyed at the study site. The Monitor will perform final IP accountability reconciliation at the study end to verify that all unused IP is adequately destroyed/returned and documented.

10 STUDY ASSESSMENTS

The study assessments are described in the sections below and the timing of these assessments are detailed in the schedule of events (Table 8.1-1, Section 8.1).

10.1 Recording of data

The Principal Investigator will provide the Sponsor with all data produced during the study from the scheduled study assessments. He/she ensures the accuracy, completeness, legibility, and timeliness of the data reported to Sponsor in the eCRF and in all required reports.

It is important that PK blood sampling occurs as close as possible to scheduled time. In order to achieve this, the timing priority order at a particular time point is:

- 1. IP pouch collection
- 2. Blood samples for PK

The time points for PK blood sampling will start from the administration of the pouch.

The plasma sample may be drawn with some deviation from the time stated in the protocol. The time window for each time point see section 10.3.1.

The actual sampling time should always be recorded in the eCRF and will be used in the calculation of the PK parameters. Pre-dose assessments may be performed up to 60 minutes prior to dosing (if not otherwise specified in the schedule of events).

10.2 Demographics and other baseline characteristics

10.2.1 Informed consent

Signed informed consent must be obtained before any screening procedures are initiated. The informed consent procedure is further described in Section 13.3.

10.2.2 Eligibility criteria

Eligibility criteria should be checked during screening and verified before randomisation/IP administration. The criteria are specified in Sections 8.6 and 8.7.

10.2.3 Demographic information

The following demographic data will be recorded: gender, age, ethnicity, race and preferred snus placement.

10.2.4 Weight and height

Weight and height will be measured without shoes. BMI will be calculated from the height and weight recorded and rounded off to the nearest whole number.

10.2.5 Physical examination

A complete physical examination will include assessments of general appearance, throat, thyroid, lungs, cardiac, abdomen (liver and spleen), lymph nodes and extremities.

10.2.6 *Medical/surgical history* CONFIDENTIAL

Medical/surgical history will be obtained by subject interview in order to verify that the eligibility criteria are met.

10.2.7 Prior and concomitant medication

Prior medication will be obtained by subject interview in order to verify that the eligibility criteria are met (see also Section 8.8.2).

Medications are classified as prior if the stop date was before or on the day of the first dose administration (pre-dose) and as concomitant if ongoing at the day of the first dose administration, stopped after the first dose administration or started after the first dose administration.

Any use of concomitant medication from screening until the last Follow-up Visit must be documented appropriately in the subject's eCRF. Relevant information (*i.e.* name of medication, total daily dose, unit, start and stop dates, reason for use if consistent with the definition of an AE) must be recorded. All changes in medication should be noted in the CRF.

10.2.8 Baseline symptoms

A baseline symptom is defined as an event that occurs between subject's signing of the ICF until the first administration of IP (i.e. an event that occurs during the screening period). Such events are not AEs and will be recorded in the medical history log in the eCRF.

10.2.9 HIV and Hepatitis B/C

Subjects will be tested for HIV and hepatitis B/C prior to inclusion into the study in order to protect personnel handling the blood samples.

10.2.10 Pregnancy test

All females of childbearing potential will do a pregnancy test (urine dipstick) at screening.

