6 INTRODUCTION

6.1 Background

Sweden has developed the lowest prevalence of smoking in Europe, particularly among males. It is widely accepted that one contributory factor to this trend is that snus has replaced cigarettes as the tobacco product of choice among many male and some female smokers.

Oral tobacco, like snus, is capable of rapidly delivering nicotine to the venous bloodstream through diffusion over the oral mucosa (Fant et al 1999) ¹. It may therefore be more satisfactory to smokers than currently available pharmaceutical nicotine replacement therapies (NRT). However, orally administered nicotine, whether in the form of snus or NRT, can never achieve the very high nicotine levels in the arterial blood to the brain that is typically associated with pulmonary delivery resulting from inhalation of tobacco smoke.

Use of smokeless tobacco is by definition unassociated with exposure to the many thousands of combustion products found in tobacco smoke (many of which are highly carcinogenic and may induce a state of systemic, chronic inflammation), or chronic irritation in the upper and lower airways resulting from the inhalation of tobacco smoke. Therefore, it is generally accepted that use of smokeless tobacco products has substantially lower health risks than cigarette smoking. However, smokeless tobacco typically entails a systemic exposure to nicotine that is comparable to that among cigarette smokers.

Nicotine is the substance that is thought to contribute the most to the addictive properties of using any type of tobacco product. Also, the nicotine exposure may help to explain the adverse pregnancy outcomes that have been observed among pregnant women who continue to use tobacco after the first trimester of their pregnancy. Such effects have been documented both for cigarette smoking and use of snus. In addition, smokeless tobacco products typically contain low levels of unwanted substances (including nitrosamines and polycyclic hydrocarbons) that have been classified as human carcinogens. So, although the health effects are substantially smaller for smokeless tobacco than for cigarette smoking, some adverse effects cannot be ruled out, in particular not effects related to the nicotine exposure.

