6.3 Risk/benefit assessment

It may be considered problematic to expose research subjects to a novel nicotine delivery product, the properties of which are not yet fully known. However, all research subjects are required to be daily snus users since at least one year (with an average or above snus consumption) so the participants are well acquainted with, and used to, the effects of nicotine.

CONFIDENTIAL

Preliminary data from previous studies indicate that the amount of nicotine extracted from the test articles is comparable to that from tobacco-based snus, despite the fact that the overall nicotine content and content of free nicotine in the ZYN® pouches is lower than in conventional tobacco-based snus (8 mg). This suggests that adverse effects from the nicotine exposure from the test and reference articles are unlikely to occur among the research subjects. So far, no adverse effects have been reported associated with the use of ZYN® apart from effects likely to be related to the nicotine exposure (such as salivation, nausea, and dyspepsia).

Aside from the nicotine, all ingredients used in the test products are food-approved (similar to ingredients in conventional snus). The nicotine in ZYN® is of pharmaceutical grade, i.e. the same as the nicotine in nicotine replacement products (gum, lozenges, mouth spray etc.). ZYN® is currently commercially available on the U.S. and Swedish markets.

The study does not involve invasive procedures, beside the collection of venous blood samples.

Pregnant women or individuals with a history of hypertension or any cardiovascular disease, who may be particularly vulnerable to nicotine exposure, are excluded from participation.

The potential adverse effects of the study procedures, which are likely to be minor and/or clinically insignificant, are from a research ethics perspective counterbalanced by the potential positive effects of the novel nicotine pouch as a reduced toxicity alternative to conventional snus. As the nicotine delivery profile of a product is likely to be central to its acceptability among current tobacco users, it is reasonable to conduct formal clinical studies to assess this feature in more detail.

Subjects will remain in the research clinic for at least 6 hours after the administration of the investigational products and will be closely monitored by medical staff.

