HIV, Hepatitis B and C	x		
Pregnancy test ³	X		
Drugs of abuse	X	x ⁴	
Alcohol screen	x	x ⁴	
CO measurement	X	x	
Randomisation		x ⁵	
IP (pouch) administration		x	
PK blood sampling		x ⁶	
Collection of pouches		х	
Treatment-emergent AEs (TEAEs)8		x	x
Baseline events	X	x ⁷	
Prior and concomitant medications ⁹	X	x	X

¹ Visit 1 could be performed during 2 days

² Refer to section 8.1.3, Schedule of Events per visit for, details.

³ Female subjects only

⁴ Drug and alcohol tests during the treatment period may be performed randomly.

⁵ Only on visit 2

⁶ Before and 5, 10, 15, 30, 60, 90, 120, 240 and 360 min after application of the investigational products

⁷Only prior to dose administration at Visit 2.

⁸ From first administration of IP.

⁹ For definitions of prior and concomitant medication, see Section 10.2.7.

Table 8.1-2 Detailed schedule of events for each treatment period

Visit					V	Visit 2 to 8	∞					
Assessment/time-point	Admission	Pre- dose	•	min 5	10	15 min	min	min	min	2 h	4 h	6
Inclusion/exclusion criteria	x ¹											
CO measurement	×											
Drugs of abuse	x ²											
Randomisation		X ³										
IP (pouch) administration			×									
IP (pouch) collection								X ⁴				
PK blood sampling		×		×	×	×	×	×	×	×	×	
Treatment-emergent AEs (TEAEs)							×					
Prior and concomitant medications						×						

¹ Confirmation of inclusion/exclusion criteria (Visit 2 only).

MW001TEMP01_02CSP

² Drug tests during the treatment period may be performed randomly
³ Only on visit 2

⁴ Collection of pouch +/- 1 (one) minute from specified time.

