8.7 Exclusion criteria

Subjects must not enter the study if any of the following exclusion criteria are fulfilled:

- 1. Smoker, defined as "smoking during the last 24 hours according to self-report and CO in exhaled air >10 ppm at clinical visits.
- 2. A history or presence of diagnosed hypertension or any cardiovascular disease.
- 3. Surgery within 6 months of the screening visit that, in the opinion of the investigator, could negatively impact on the subject's participation in the clinical study.
- 4. Any surgical or medical condition, which, in the judgment of the clinical investigator, might interfere with the absorption, distribution, metabolism or excretion of the investigational product.
- 5. History of any clinically significant disease or disorder which, in the opinion of the Investigator, may either put the subject at risk because of participation in the study, or influence the results or the subject's ability to participate in the study.
- 6. Breast feeding, pregnancy or planning to get pregnant during the study.
- 7. Female use of systemic contraceptives (such as oral contraceptives, implants, injectable steroids, vaginal ring, transdermal patch).
- 8. Any positive result on screening for serum hepatitis B surface antigen, hepatitis C antibody and Human Immunodeficiency Virus (HIV).
- 9. Positive screen for drugs of abuse or alcohol at screening or on admission to the unit prior to administration of the IP.
- 10. Current or history of alcohol abuse and/or use of anabolic steroids or drugs of abuse.
- 11. Plasma donation within one month of screening or blood donation (or corresponding blood loss) during the three months prior to screening.
- 12. Investigator considers the subject unlikely to comply with study procedures, restrictions and requirements.

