8.8.1 General restrictions

- Subjects shall abstain from snus and all other nicotine containing products from 8.00 p.m. the night before each study day.
- Subjects shall abstain from smoking the last 24 hours before each study day.
- The subjects are not allowed to eat or drink or use any other mouth related procedure (e.g. tooth brushing) 30 minutes before dose administration, during application of investigational products and 30 minutes after the investigational product have been taken out. ³.
- The female volunteers are expected to be sexually abstinent or use non-systemic contraceptives to prevent pregnancy during the study period.

- Abstain from use of Methyl salicylate containing products, e.g. ointments, mouth wash and chewing gum.
- Abstain from drugs of abuse from Screening to the Follow-up visit.
- The subjects must not donate blood or plasma during the study until three months after the Follow-up Visit.
- Study subjects are not allowed to participate in any other clinical study during the study period i.e screening to follow up.

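### The only pregnancy test is the screening dipstick, so its result is 1 to 28 days old when the pregnancy exclusion is verified at Visit 2 before the first dose

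*Protocol*

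**What the plan says.** - **The test.** Protocol section 10.2.10: "All females of childbearing potential will do a pregnancy test (urine dipstick) at screening". Table 8.1-1 marks it in the Visit 1 column only, with a window of Day -28 to -1. Table 8.1-2, the detailed schedule for Visits 2 to 8, has no pregnancy row.
- **The first dose.** Section 8.11: "On study Day 1 (Visit 2), the subjects will be randomised to a treatment sequence".
- **The eligibility check.** Section 10.2.2: "Eligibility criteria should be checked during screening and verified before randomisation/IP administration". Footnote 1 to Table 8.1-2 places this confirmation at Visit 2 and at no later visit.
- **The exclusion.** Section 8.7, criterion 6: "Breast feeding, pregnancy or planning to get pregnant during the study".
- **The reason for it.** Section 6.3 says of pregnant women, and of people with hypertension or cardiovascular disease: "who may be particularly vulnerable to nicotine exposure, are excluded from participation".
- **Contraception.** Section 8.7 criterion 7 and section 8.8.2 bar systemic contraceptives. Section 8.8.1 states what remains: "The female volunteers are expected to be sexually abstinent or use non-systemic contraceptives to prevent pregnancy during the study period".
- **If pregnancy occurs.** Section 10.5.9 stops treatment at once and withdraws the subject on pregnancy or on suspicion of it.

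**The concern.** The protocol treats pregnancy as an absolute exclusion, relies on it in the risk/benefit argument, and requires the exclusion to be verified just before dosing. The only objective evidence available at that check may be four weeks old. A woman who conceives after the screening test and has not noticed could pass the Visit 2 check, be randomised, and receive up to seven single doses with nominal nicotine content between 6 and 18 mg (Table 6.1-1). The protocol intends that she should not take part.

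What is at stake is subject protection. No estimate, test or sample-size figure depends on it.

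**Working it through.** **Inputs**
- Test day *d*: any day from -28 to -1 (Table 8.1-1; section 10.2.10).
- Verification, randomisation and first dose: Visit 2 = Day 1 (sections 8.11 and 10.2.2; Table 8.1-2, footnote 1).
- Maximum number randomised: 36 (synopsis).
- Number of women of childbearing potential: not given.

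**Age of the result at Visit 2**

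Assume the usual numbering with no Day 0, so that Day -1 is the day before Day 1. Then age = -*d*.
- Test on Day -1: 1 day.
- Test on Day -28: 28 days.
- Range: 1 to 28 days.

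If a Day 0 were counted, age = 1 - *d*, which gives 2 to 29 days. With a dipstick at Visit 2 admission the age is 0 days.

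**Age at later sessions**

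The result only gets older over Visits 3 to 8. The protocol is not explicit about what its approximate 7 weeks covers, so both readings are assumptions:
- If it includes screening and the 7-day follow-up, the result is at most about 7 - 1 = 6 weeks old at the last dose.
- If it is treatment time only, the upper limit is 28 + 49 = 77 days, or about 11 weeks.

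**What the Visit 2 check can draw on**

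| Criterion | Evidence scheduled or allowed after screening |
|---|---|
| Smoking (criterion 1) | CO measured at every session (Tables 8.1-1 and 8.1-2) |
| Drugs and alcohol (criterion 9) | Criterion covers a positive screen on admission; random repeat tests allowed (sections 10.2.11 and 10.2.12) |
| Pregnancy (criterion 6) | None |

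For pregnancy, the verification at Visit 2 and the stop rule in section 10.5.9 both apply. Neither comes with a current test, so both depend on the woman's report or on suspicion.

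**Number of extra tests under the fix**

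One per woman of childbearing potential who attends Visit 2: between 0 and 36 among those randomised, plus any woman whom the test itself excludes.

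**The case against.** The case on the other side is substantial.

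- **The interval is not unprotected.** Criterion 6 also excludes women who plan a pregnancy. The requirement for abstinence or non-systemic contraception runs from screening to follow-up (sections 8.8 and 8.8.1), so it covers exactly the days between test and first dose. Suspicion alone stops treatment. This stands, and it makes the event less likely. It does not provide a current test result at the check.
- **The subjects are established snus users.** They use at least two cans a week (section 8.6) and must abstain only from 8 p.m. the evening before each session. Excluding a woman at Visit 2 would not stop her own use. This also stands: a net increase in nicotine exposure is not shown. What remains is that the trial itself would dose a person it has excluded.
- **The remedy is partial.** One test at Visit 2 does nothing for conceptions during Visits 3 to 8. The 0-day figure describes the age of the result and not the number of pregnancies detected. That is correct and limits the benefit without removing it.

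Two stronger readings are tempting, and the protocol supports neither.

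- A reader might infer that section 10.2.2 contradicts section 10.2.10. It does not. It asks for eligibility to be verified and does not ask for any test to be repeated. The text and both tables agree on one test.
- A reader might cite section 6.1, which says that "the nicotine exposure may help to explain the adverse pregnancy outcomes that have been observed among pregnant women", as evidence of harm. The sentence goes on to limit this to women whose tobacco use continues beyond the first trimester. It therefore does not speak to a few single doses in the first weeks after conception. The point has to rest on section 6.3, criterion 6 and the Visit 2 verification.

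**Conclusion.** The point holds as a minor weakness in the schedule that the protocol fixes. At the moment when exclusion criterion 6 must be verified, the pregnancy result is 1 to 28 days old (assuming no Day 0), and the check rests on self-report or suspicion while systemic contraception is barred.

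The calendar facts are firm. The likelihood of an unrecognised pregnancy at Visit 2 cannot be quantified from the protocol, and neither can the gain from a second dipstick. The primary endpoint and its analysis are unaffected. This is an inexpensive improvement worth considering and not a defect that puts the trial's conclusions in doubt.

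**What to change.** Add the same urine dipstick for females of childbearing potential at Visit 2 admission, before randomisation and first dose. State it in section 10.2.10, mark it at Visit 2 in Table 8.1-1, and add a Visit 2 row to Table 8.1-2.

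The cost is a small protocol amendment and one dipstick per such woman, at a visit that already takes place and at which urine drug testing is already allowed. No new visit or staff is needed. The downside is an occasional exclusion at Visit 2. Conceptions after Visit 2 would still rely on the contraception restriction in section 8.8.1 and the stop rule in section 10.5.9.
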